	Baseline	Post- treat.	3 mo F/U	12 mo F/U
Part 1				
Demographics questions	✓			
Self-Administered Comorbidity Questionnaire + 32 additional items	√			
WatchPAT overnight home sleep monitoring	\checkmark			
Mini-Mental State Examination (MMSE)	\checkmark			
Part 2				
Mini-International Neuropsychiatric Interview (MINI)	✓			
PTSD Checklist for DSM-5 (PCL-5)	✓	✓	✓	
Patient Health Questionnaire - GAD-7	\checkmark	\checkmark	\checkmark	
Anxiety Sensitivity Index -3 (ASI-3)	\checkmark	\checkmark	\checkmark	
Restless Legs Syndrome (RLS) questionnaire	\checkmark	\checkmark	\checkmark	
Epworth Sleepiness Scale (ESS)	✓	\checkmark	✓	
Brief Pain Inventory	✓	\checkmark	 ✓ 	
Nighttime urination questions	✓	\checkmark	✓	
Wrist actigraph (7 days)	\checkmark	\checkmark	\checkmark	
Sleep diary	\checkmark	\checkmark	\checkmark	
Part 3				
Insomnia Severity Index	✓	\checkmark	 ✓ 	
Pittsburgh Sleep Quality Index	✓	\checkmark	✓	
DSM-5 diagnostic criteria questions	✓	\checkmark	 ✓ 	
Disturbing Dream/Nightmare Severity Index (DDNSI)	✓	\checkmark	\checkmark	
Glasgow Sleep Effort Scale	✓	\checkmark	✓	
WHO-QOL BREF	✓	\checkmark	\checkmark	
European Quality of Life Scale (EQ-5D)	✓	\checkmark	✓	
Calgary Sleep Apnea Quality of Life Index (SAQLI)		\checkmark	 ✓ 	
PHQ-9	\checkmark	\checkmark	\checkmark	
Flinders Fatigue Scale (FFS)	\checkmark	~	\checkmark	
Perceived Stress Scale (PSS)	\checkmark	\checkmark	\checkmark	

Table 5: Measures at each data collection timepoint

Medications taken during week wearing actigraph	✓	~	✓			
Healthcare utilization questionnaire	✓	~	\checkmark			
Remote telemonitoring of nightly PAP use		\checkmark	✓	✓		
PAP use data		~	✓	✓		
Everyday Discrimination Scale	✓					
Major Experiences of Discrimination Scale		✓				

The Brief Pain Inventory (BPI)-Short Form:²⁴ is a 9-item version of the BPI which measures pain severity, treatments, and daily interference over the past week. The BPI has been validated and is sensitive to changes over time.

Nightttime urination, including number of times participant gets up to urinate, and a rating of how bothersome getting up at night is, will be asked at each assessment timepoint.

Medications will be abstracted from medical records and participants will be queried about use of over-thecounter, herbal and non-VA prescription medications. Sleep medication use will be tracked within the daily sleep diary at baseline, post-treatment and 3-month follow-up. Medication data will be coded by drug class, focusing on psychotropic medications that may affect sleep, and summarized categorically (i.e., use/non-use). We will look at sedating medications taken at bedtime, including hypnotics, sedating antidepressants, sedating antipsychotics and antihistamines.

Psychiatric conditions/symptoms/quality of life:

The Mini-Mental State Examination (MMSE) will be used to measure baseline cognitive status in participants aged 65 years and older. This scale assesses orientation, registration, attention/ calculation, recall, language and construction, and has standard instructions. MMSE responses will be used in evaluating appropriateness for randomization.

The Mini-International Neuropsychiatric Interview (MINI)²⁵ is a standardized structure interview for diagnosing DSM-5 lifetime and current Axis I mental disorders. The MINI will be administered by trained clinicians (Drs. [name], [name]). Women will not be excluded due to presence of mental health conditions; however, this will be considered an important descriptive variable and will be used for conducting sub-group analyses of patients with specific comorbidities.

The PTSD Check List for DSM-5 (PCL-5)²⁶ is a standardized assessment for PTSD, based on DSM-5. A Life Events Checklist will be used to identify traumas experienced by women Veterans, and the most distressing event will be used for completion of the PCL.

The Generalized Anxiety Disorder-7 (GAD-7)²⁷ will be used to assess anxiety symptoms.

The Patient Health Questionnaire-9 (PHQ-9)²⁸ is a 9-item depression module in the PHQ, which is part of the Primary Care Evaluation of Mental Disorders (PRIME-MD) suite of evaluation tools. The PHQ-9 is widely used to screen for depression across VA.

The Perceived Stress Scale (PSS)^{28a} is a global measure of stress. The 14-item scale measures how unpredictable, uncontrollable and overloaded respondents feel about stressful situations in the previous month. Responses are chosen from a 5-point Likert scale.

The WHOQOL-BREF²⁹ is a 26-item version of the WHOQOL-100, and is frequently used as a quality of life outcome measure in clinical trials. The questionnaire includes four domains: physical health, psychological health, social relationships and environment. It also includes one question on overall quality of life and one on general health.

The European Quality of Life Scale (EQ-5D)^{29a} is a measure of health-related quality of life that can be used in a wide range of health conditions and treatments. It contains 5 dimensions: mobility, self-care, usual activities, pain/discomfort and anxiety/depression.

The Calgary Sleep Apnea Quality of Life Index (SAQLI)^{29b} is a 35-item questionnaire that evaluates 4 domains of quality of life associated with sleep apnea: daily functioning, social interactions, emotional functioning, symptoms, and treatment-related symptoms (for individuals using PAP therapy).

The Anxiety Sensitivity Index-3 (ASI-3)³⁶ is an 18-item questionnaire that measures fear of anxiety-related sensations based on beliefs about their harmful consequences. The ASI-3 has 3 6-item subscales that measure physical, cognitive, and social concerns.

Everyday Discrimination Scale: is a 9-item measure of daily discrimination as it relates to gender or race/ethnicity, assessed from "never" to "almost every day." A total score is computed by summing all items.

Major Experiences of Discrimination Scale: is a 9-item measure assessing the last time a person experienced discrimination ranging from "past week" to "one year ago" and frequency of experiences of discrimination over the person's lifetime (total number).

Medical record review:

A structured medical record review will be performed at baseline and at the 3-month follow-up assessment to obtain information on health history and utilization of VA healthcare services, including outpatient visits in the 90 day period prior to study enrollment, and inpatient stays in the prior year. Problem list diagnoses and prescribed medications will be abstracted to inform randomization eligibility decisions (at baseline) and gather descriptive data about participants at 3-month follow-up.

Sleep Measures:

We will use unattended home sleep apnea testing (HSAT) to assess SA. In the past, SA was largely diagnosed with overnight laboratory polysomnography (PSG); however, this method has several limitations including cost and inconvenience. As an alternative to PSG, there are commercially-available devices to assess SA in the home. Although there are limitations to HSAT, VA has been an early adopter of HSAT. Our experience with women Veterans suggests that attended laboratory PSG, which entails observation by a (usually male) technician during sleep, is a significant barrier to SA diagnosis. Some women would also incur additional burden due to overnight childcare needs during laboratory PSG. HSAT is also less expensive, enabling us to study a larger group of women.

We will use the WatchPAT system (Itamar Medical, Caesarea, Israel) HSAT, because of its validity, reliability, ease of use, comfort, and low cost. This wrist-mounted system has an embedded actigraph to estimate sleep, fingertip sensors for measuring peripheral arterial tone (PAT) and pulse oximetry, and a reusable snoring/body position sensor. The system measures respiratory disturbances based on PAT (a reflection of autonomic nervous system changes) and pulse oximetry during sleep. Compared to laboratory PSG, studies have demonstrated a correlation of r=.85-.96 for respiratory disturbance index (RDI) and AHI.

Participants will review a brief video describing the WatchPAT device, the opportunity to practice with the WatchPAT sensors and to ask questions. They will be given an instruction booklet and a 24-hour toll-free company-supported advice line to call if difficulties arise overnight.

The 4-item Restless Legs Syndrome (RLS) questionnaire³⁰ will be used to identify significant RLS as well.

The Pittsburgh Sleep Quality Index (PSQI)³¹ assesses sleep quality and disturbances over the past month. The PSQI is sensitive for distinguishing normal and abnormal sleepers and has good test-retest reliability. We will use the 3-factor scoring, which has been shown to have superior psychometric properties.

The Insomnia Severity Index (ISI)³² is a 7-item instrument using Likert-type scales to measure severity of insomnia symptoms. The ISI correlates well with scores on the PSQI (r=.67), and with sleep diary measures (r's=.32-.91).³¹

The Epworth Sleepiness Scale (ESS)^{31a} An 8-item questionnaire measuring level of daytime sleepiness, based on likelihood of dozing off or falling asleep in specific situations (e.g., reading, watching television).

The Disturbing Dream/Nightmare Severity Index (DDNSI)^{31b} is a 5-item index that measures severity and intensity of nightmares on a 0-4 Likert-type scale. A score greater than 10 may indicate the presence of a nightmare disorder.

The Glasgow Sleep Effort Scale^{31c} is a 7-item scale that measures perceived effort to fall asleep over the past week.

The Flinders Fatigue Scale (FFS)³³ is a 7-item scale used to measure general symptoms of fatigue. The FSS is sensitive to change after sleep-related interventions and will be used as an outcome measure.

Four of the DSM-5 diagnostic criteria questions that address length of time having sleep problems and adequate opportunity and circumstances to sleep will be asked.

Participants will complete daily sleep diaries based on the American Academy of Sleep Medicine Consensus Sleep Diary, which we adapted using a cognitive interviewing process with women Veterans, at baseline, post-treatment and at the 3-month follow-up. PSQI, ISI and sleep diaries will be used as measures of subjective sleep quality.

Wrist actigraphy will be used to objectively measure sleep. Participants will wear an actigraph (Actiwatch 2, Minimitter/Respironics, Bend, OR) on the non-dominant wrist for one week. The actigraph is a small watchsized device useful in longitudinal, naturalistic assessment of sleep patterns.^{34,35} Actigraphs contain accelerometers which measure movement. In general, movements below an established threshold is interpreted as sleep while high activity is interpreted as wakefulness. Commercially available software uses validated algorithms to determine minute-by-minute sleep vs. wake. Actigraphy has been validated in numerous studies, and evidence-based guidelines direct use of this technology. Agreement between wrist actigraphy and PSG in young and older people is .89-.95. We have developed highly standardized research procedures and protocols for use and scoring of actigraphy, and we have trained, experienced members of our research team to apply these protocols. In our work with women Veterans, actigraphy has been well-tolerated, with less than 2% missing data. We will analyze actigraphy data defining "night" and "day" based on sleep diary-reported bedtimes and rising times.

Potential Risks:

None of the procedures within this study are high risk; however, there are a number of minor risks, which will be minimized to the extent possible.

Sleep monitoring devices: The known risks associated with wearing the sleep monitoring devices are minimal. The sleep apnea sensors worn for one night and the sleep watch worn for 8 days may be annoying or uncomfortable. Rarely, they may cause skin irritation or an allergy. We have extensive experience using wrist actigraphy and the WatchPat system, and have chosen these devices because they are well-tolerated by participants. They are also substantially less burdensome than other objective methods of recording sleep (i.e., requiring the participant to spend a night in a sleep laboratory). Research staff will review carefully with participants potential skin problems associated with wearing the wrist actigraph and the WatchPat. Participants will be told to remove the device if they have any significant discomfort or any evidence of skin injury. Participants will have access to a research staff person 24 hours a day, in case they have questions or concerns about the equipment. In addition, the company which makes the WatchPAT device has a 24-hour advice line that also provides troubleshooting support. Our monitoring devices are checked regularly to insure safe and proper operation. The PI will be notified immediately of any significant discomfort experienced by study participants.

Questionnaires: Some participants may find completion of the questionnaires tedious or tiring, or may find other mental discomfort in answering some items. To lessen the risk of mental discomfort among participants, research staff will be trained to recognize discomfort in participants, and they will be trained to remind participants of the voluntary nature of the research and that they may refuse any portion of the study.

Sleep apnea education program: Participants may find that coming to the 6 education sessions is tiring or inconvenient. In addition, adjustments to the participant's sleep habits may result in some initial daytime sleepiness. The education sessions will be scheduled at times that are convenient for participants and will only last 45 minutes or less. Conducting the session over the telephone will be offered for participants who have unexpected difficulties in coming to the VA. Participants will be advised that they may experience daytime sleepiness as a temporary result of their modified sleep schedule (e.g., reduced daytime napping and maintaining a regular bedtime and wake up time) and it will likely resolve within one week.

Safety Monitoring Plan:

Since this study does not include any investigational drugs or devices, and carries only minimal risks, we will not have a formal safety monitoring board as required for FDA studies. However, we have developed a procedure for monitoring and reporting any study-related adverse events among the women who we meet face-to-face.

Step 1: If a participant reports a study-related adverse event, research staff will report this to the Principal Investigator ([name]) as soon as possible (always within 24 hours). When [name] is unavailable, [name] (study co-investigator) will be contacted.

Step 2: If indicated, [name] will speak with the participant to determine the severity and likely cause of the concern. If medical examination is needed, the participant will be advised to go to the VA outpatient clinic and their VA primary care provider will be notified (by phone or by medical record research notes).

Step 3: [name] will report the event to the IRB and will make a determination whether study protocols should be modified for that participant, whether the participant should be withdrawn from the study, or whether the study protocols should be modified overall.

Step 4: All concerns reported by research staff will be documented, whether or not they appear to be studyrelated, and will be reviewed monthly by Drs. [name] and [name].

In the event that a participant expresses a serious medical or psychiatric concern, research staff will immediately contact [name] or [name], or if they are unavailable, will escort the participant to the Emergency Room (or outpatient clinic), or dial 911. All research staff are trained annually on participant safety issues, have the phone numbers of the Veterans Crisis Line, and have access to clinicians to assist with urgent safety concerns should they arise.

Sample size estimates

We anticipate sending 2,000 recruitment letters over the course of the study. Based on recent experience with similar methods, we expect 20% (n=400) will "opt out" of being contacted, 15% (n=300) will not be reachable by phone, and 20% (400) will refuse telephone screening. Based on these estimates, 900 women will be screened by phone. We estimate that 80% of women will meet criteria for the study (n=720) and approximately 40% of these women will be enrolled into the study (n=300). Given that women will be identified as having one or more SA risk factors, we anticipate that 45% (n=130) will have SA after objective testing. We expect that an additional 20% will not meet the final set of study inclusion criteria for randomization (described below) or will refuse further participation after completion of baseline. This will leave a total of 104 women potentially appropriate for randomization. To address the study aims a total of 90 women will need to be randomized. If we are unable to meet enrollment or randomization targets using these criteria, we will expand our list of SA risk factors extracted from the CDW (e.g., heart disease, depression).

Data management and analysis

Each participant will be assigned a unique ID which will be entered into electronic files and used on study forms. Using existing protocols, we will secure paper records and electronic data files in compliance with VA data security policies. All data will be coded by the data manager, then entered into databases using procedures established in prior work to minimize errors. Datasets will be cleaned by screening for out-of-range values, and comparing a random sample of 10% of entered data to original data forms. Double entry procedures will be used on a second, 10% random sample of cases in each dataset, with additional training and review of data if errors are identified. Cleaned data will be scored and aggregated, then data will be merged into one main database for analyses. Analyses will be preceded by a thorough inspection of data, scrutinizing for out of range values, implausible values, and outliers. Statistical assumptions for all tests will be assessed (e.g., for example, linearity and homogeneity of regression for the ANCOVA analyses).

Study Design Considerations: Study design and analysis will follow CONSORT guidelines. Participants will be randomly assigned to ABC-SA or control, and adequacy of randomization will be assessed by comparing groups on baseline measures. We will follow intention-to-treat (ITT) principles. We will collect follow-up data from all randomized patients whether or not they complete the intervention to which they are assigned. Since PAP adherence data will be gathered remotely using tele-monitoring technologies (PAP machines transmit data to a cloud-based server), complete data (including confirmed non-use) is expected for each person for all 12 months. In a previous study, PAP adherence data or confirmed non-use has been obtained in 100% of participants. Based on our recent work with women Veterans, we anticipate 20% of participants will have missing or incomplete data at the 3-month follow-up. To improve retention, participants will be offered compensation for follow-up assessments, regardless of whether they complete the intervention. While we do not anticipate differential attrition, we will compare completion rates between groups and we will compare baseline characteristics between those with complete vs. incomplete follow-up data to test for systematic attrition. To preserve the equivalency formed by randomization (and since ITT analysis requires complete

data), missing data will be imputed using multiple imputation. Sensitivity analyses will be performed comparing the ITT results (with imputation) to results for those with complete data only. For outcomes other than PAP adherence, we have allowed for 20% missing data in sample size computations [N=72 (36/group) at 3-months follow-up]. Significance tests will use two-tailed tests and alpha=.05. Power analyses are computed using two-tailed tests, alpha=.05, and power=80%. When assessing power, Cohen's d is used to describe the size of an effect, which can be detected for the specified sample size and power. For tests comparing two groups, Cohen's d=of .20 is described as small, .50 as medium, and .80 as a large effect.

Aim 1 Data analysis/sample size calculations: Aim 1 examines effects of ABC-SA on PAP adherence. We will compute the proportion of nights (out of 30 nights) with \geq 4 hours of PAP use per month. PAP adherence will be computed for the first 30 days (month 1), and for each subsequent 30-day period (months 2-12). The proportion of nights a patient uses PAP \geq 4 hours will be computed by summing nightly scores (1=PAP use \geq 4 hours; 0=PAP <4 hours) and dividing by the number of nights (i.e., 30). Denoting \hat{p}_{ij} as the proportion of nights for person *j* in month *i*, the sampling distribution of \hat{p}_{ij} will have an expected value of p_i (the true proportion who use PAP in the population in month *i*) and the SD of this sampling distribution is sqrt(N*p_i *(1-p_i)). Based on the central limit theorem, the sampling distribution of these monthly proportions, \hat{p}_i is expected to be normal, justifying use of normal theory statistics for analysis of monthly adherence.

Data analysis: For Hypotheses 1a and 1b, mixed-effects models will be used to compare monthly PAP adherence for ABC-SA vs. control. When applied to longitudinal designs, mixed-effects models permit specification of a wide variety of residual covariance structures. PAP adherence will be analyzed using a 2X12 factorial mixed-effects model with a fixed intercept.⁷⁸ Treatment group will be the 2-level between subjects factor and time (months) will be a 12 level categorical repeated measures factor. This approach will allow us to examine potential non-linear trends, which would not be apparent if time were treated as a continuous variable. The Bayesian Information Criteria (BIC) will be used to identify and select the best fitting residual covariance

structure. Using the mixed-effects model, the difference in adherence rates between the ABC-SA and control groups will be assessed and tested at each month. To understand the nature of the treatment effects, we will dissect the "time by treatment" interaction into a series of tests of the simple effect of the treatment effect at each month. Figure 2 illustrates four possible patterns of results. Consistently significant treatment effects is consistent with Pattern 1. Significant treatment effects in early months, followed by non-significant effects in later months is consistent with Pattern 2. Nonsignificant treatment effects in early months, followed by significant treatment effects in the remaining months is consistent with Pattern 3. Lastly, finding significant treatment effects in the middle months, but not early and later months is consistent with Pattern 4.

Power Analysis: Power was computed assuming complete data (N=90; 45/group). Analyses focus on the treatment effect (ABC-SA vs. control) in terms of the proportion of nights with PAP use >4 hours per month; thus, the power analysis shows the power to detect differences in the proportion of nights of PAP use >4 hours per month between ABC-SA and control groups. The SD of this proportion is conservatively estimated as SD=.091 [computed as sqrt(.5*(1-.5)/30)=.0913]. Given this SD, alpha=.05 and power=.80, the study can detect a difference in the average proportion of nights of PAP use \geq 4 hours as small as 5.5% between ABC-SA and control for a given month. In interpreting the results, we will focus on larger, more clinically-important effects. This study will have ample power to detect clinically meaningful effects. The power to detect a 7.5% difference in adherence rates between groups would be .97. The power to detect a 20% difference would exceed .99. We would consider a difference of 10-15% to be clinically significant, and an effect >15% to be of substantial clinical importance. Results will be interpreted with these benchmarks in mind.

Aim 2 Data analysis/Sample Size Calculation: Aim 2 compares outcome measures that we expect to improve with improved PAP adherence. Outcomes tested are objectively measured (Aim 2a) and self-reported

(Aim 2b) sleep quality. The sample size for these analysis is expected to be N=72 (n=36 per group), accounting for 20% missing data from the 90 randomized participants.

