Initial screening for SA will be part of research activities in this study. However, the diagnosis of SA and any prescription for SA treatment will occur within the VA GLA Sleep Disorders Center (SDC) and will be documented in the participant's VA medical record. Following a process previously used in [name] study (project #0015) and approved by [name] (SDC Director and co-investigator), SDC physicians will review WatchPAT results. The reviewing physicians will determine whether the participant has sleep apnea based on International Classification of Sleep Disorders definition⁶⁷ or requires additional testing (e.g., repeat of a home sleep test or a laboratory polysomography (PSG)). Following standard clinical practices, the participant will be informed of her diagnosis by an SDC physician or other clinic staff member, who will discuss treatment options. The treating physician will prescribe the appropriate treatment and establish the initial pressure settings for PAP for patients who accept this treatment.

Eligibility determination for randomization

Participant's baseline assessment results will be reviewed during a weekly investigators' meeting to determine eligibility for randomization to receive the study intervention. The meeting will include [name] (a psychologist *Study protocol* 6 Version: 2/24/2021

specializing in Behavioral Sleep Medicine) plus one of the Board Certified Sleep Medicine physicians (Drs. [name], [name] or [name]), and a member of the study team who completed baseline assessments. These investigators will review the baseline assessment and medical record to determine if a participant meets the inclusion criteria for randomization (AHI>5 from overnight sleep apnea recording, a diagnosis of SA and a prescription for PAP therapy) and does not meet any of the following exclusionary criteria that would make them ineligible for randomization:

- (1) no SA (AHI<5) found on overnight monitoring
- (2) another untreated sleep disorder that accounts for sleep difficulties (e.g., untreated restless legs syndrome)
- (3) unstable medical or psychiatric conditions (e.g., chemotherapy, untreated schizophrenia)
- (4) prior participation in a structured PAP adherence program or our ABC-I intervention
- (5) no sleep-related complaints or symptoms on baseline assessments
- (6) refusal to attempt PAP therapy

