Participants with stable psychiatric/medical conditions, and those using medications for sleep will not be excluded. Participants determined to be ineligible for the study will be notified by mail (see Participant Ineligibility Letter).

Randomization

Participants approved for randomization will be randomly assigned to the ABC-SA (n=45) or control program (n=45), following CONSORT guidelines.⁴⁷ Randomization sequences will be created using a computerized random number generator. Stratified randomization will help insure that groups (ABC-SA and control) are balanced in the severity of SA (AHI 5-15, and AHI>15). Furthermore, within each strata, the randomization sequences will be "blocked" using a block size of n=4. The study statistician will generate the stratified randomization sequence and transfer it to a series of "security envelopes". These envelopes, containing the group assignment, will be stored in a secure location that only authorized "unblinded" staff can access. This will assure random allocation concealment, which is critical to the integrity of randomized trials.

Study groups

• ABC-SA for women Veterans with SA (Table 4)

Participants randomized to ABC-SA group will receive the Acceptance and the Behavioral Changes to treat Sleep Apnea (ABC-SA) program that we developed to improve PAP adherence among women Veterans. The ABC-SA program melds strategies to improve sleep (stimulus control, targeted sleep hygiene, sleep compression) and increase PAP adherence (SA and PAP education) with psychological principles of ACT (e.g., using metaphors, linking behavior change to values, strategies for accepting discomfort). The program includes 6 weekly face-to-face meetings with the study interventionist, plus ongoing monitoring and support. Sessions are designed to last <45 minutes each. Issues specific to women's health are incorporated into ABC-SA, such as discussion of social factors that might impact PAP adherence (e.g., interpersonal relationships) and health issues among women (e.g., heart health, menopause and SA). Sessions are interactive to facilitate participant engagement. A written outline with the specific, individualized recommendations documented in clear language will be provided after each session. Interventionists will also complete session summaries for the participants to review at home.

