Dysfunctional Beliefs and Attitudes about Sleep – 10 item (DBAS-10):²⁰ The DBAS-10 is an abbreviated version of the original 28-item DBAS examining beliefs about the immediate and long-term negative consequences of insomnia as well as beliefs about the need for control over insomnia. This 10-item version has been shown to be well correlated (r=0.83) with the full scale and sensitive to cognitive changes resulting from cognitive-behavioral therapy for insomnia. Key variables: DBAS total score.

Sleep Hygiene Index (SHI)²¹ The 13-item sleep hygiene index is based on diagnostic criteria for inadequate sleep hygiene, and has superior reliability compared to other (typically longer) sleep hygiene questionnaires (Chronbach's α =0.66). This measure will be used to identify sleep hygiene related behaviors, including the use of alcohol, caffeine and tobacco within 4 hours of bedtime. Key variable: SHI total score.

Credibility/expectancy questionnaire (CEQ):²² The CEQ is a 6-item questionnaire used both at the beginning and end of treatment. This questionnaire will be administered at the end of the first treatment session and again at the end of the final treatment session in both groups. Since this measure cannot be used until the individual understands the type of treatment she will receive, it will not be assessed until after session 1 when information about the treatment is available. The post-treatment items will be administered at the end of the final treatment session 6). Differences in scores between the groups will be explored. Key variable: CEQ total scores at the beginning and end of treatment.

Treatment sessions will also be audio recorded and one of the study investigators will listen to and rate sessions using a Fidelity Monitoring Form to assess adherence to the intervention content and competency of the study interventionist.

COVID-19 amendment for intervention /control sessions

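### A single disclosed block size of 4, with nothing to keep investigators who learn assignments out of the eligibility meeting, leaves a route to predicting allocations

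*Combined protocol and SAP*

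**What the plan says.** The Randomization section assigns 45 women to each programme, stratified by AHI (5 to 15, and above 15), with sequences blocked "using a block size of n=4". No other size and no variation is described. The statistician prepares the sequence and puts it in envelopes that only authorized unblinded staff can reach. The section concludes that this assures concealment.

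Under Eligibility determination for randomization, a weekly investigators' meeting reviews baseline results "to determine eligibility for randomization to receive the study intervention". It consists of a psychologist, a sleep physician and the team member who did the baseline assessments. The inclusion criteria it applies are "AHI>5 from overnight sleep apnea recording, a diagnosis of SA and a prescription for PAP therapy", so the meeting sees the AHI and hence the stratum. Three of the exclusions call for judgement: whether another sleep disorder explains the complaints, whether a medical or psychiatric condition is unstable, and whether there are no sleep complaints.

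At the end of Intervention process measures, sessions are audio recorded and "one of the study investigators will listen to and rate sessions using a Fidelity Monitoring Form". Under Follow-up assessments, the staff who carry out those assessments are said to be blinded. No such statement covers the eligibility meeting.

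**The concern.** Concealment requires that whoever decides to admit a woman cannot foresee her arm. Secure envelopes meet only half of that requirement. With a known block size, the arms already used in a block limit those still to come, and no one needs to open an envelope.

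A recording gives the arm away. ABC-SA uses metaphors, values work and review of the woman's own PAP data, while the control programme gives nondirective information. If a person who has learned arms this way also helps decide eligibility, a borderline woman could be admitted or turned away with her likely arm in mind.

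The primary outcome, nightly PAP use, plausibly depends on which women are admitted. The Aim 1 mixed model has treatment and month as its factors and names no baseline covariate. Adjustment could reduce imbalance in recorded characteristics, but not selection on unrecorded impressions.

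**Working it through.** The plan gives no figure for predictability, so there is none to reproduce.

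**Inputs from the protocol.** Block size 4; ratio 1:1, so each block holds 2 + 2; two AHI strata; 90 women (Sample size estimates: "To address the study aims a total of 90 women will need to be randomized").

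**Full knowledge of earlier arms in the stratum (worst case).** A 2 + 2 block has 6 equally likely orderings. An allocation is certain once one arm is used up.
- In 4 orderings only the last place is certain; in the other 2 (AABB, BBAA) the last two are. Certain places: 4×1 + 2×2 = 8 of 24 = 33.3%.
- By place, the chance of certainty is 0, 0, 1/3 and 1. The chance that the best guess is right is 1/2, 2/3, 2/3 and 1, with mean (0.500 + 0.667 + 0.667 + 1.000)/4 = 17/24 = 70.8%, against 50% by chance.
- For 90 women, assuming 45 per stratum: each stratum has 11 complete blocks and one woman over, so 2 × 11 × 4/3 = 29.3 of 90 = 32.6% are certain on average.

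**Partial knowledge.** The documents do not say how many sessions are rated or when, so a range is needed. Assume the observer knows the position in the block and a random share *f* of earlier arms.
- Third place is certain with probability f²/3 (both earlier arms known, and equal).
- Fourth place is certain with probability f³ + 3f²(1−f)/3 = f² (all three known, or exactly two known and equal).
- Average over the four places: (f²/3 + f²)/4 = f²/3.

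| Share of earlier arms known (assumed) | Certain | Best guess right |
|---|---|---|
| 25% | 2.1% | 55% |
| 50% | 8.3% | 60% |
| 100% | 33.3% | 71% |

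**Delayed knowledge.** If all arms become known but one allocation late within the stratum, only the fourth place can be certain, with probability 1/3. That gives (1/3)/4 = 8.3% certain and (0.500 + 0.500 + 0.667 + 0.667)/4 = 58% guessed right. Two allocations late, nothing is certain and 54% are guessed right.

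**Varying block sizes, full knowledge.** Simulation assumptions: sizes 4, 6 and 8 equally likely in random order; the observer knows the possible sizes but not their order, and updates after each allocation; 45 per stratum; 4,000 runs. About 2% of allocations are certain and about 67% are guessed right. Fixed blocks of 4 in the same set-up give 32.6% and 70.4%.

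**End-of-stratum imbalance.** An unfinished block of 4 can leave the arms 2 apart; an unfinished block of 8 can leave them 4 apart.

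**The case against.** A computer-generated, stratified, blocked list held by the statistician, with restricted envelopes, is a recognised design, and naming the block size contradicts nothing else in the plan. The reference to unblinded staff implies that others are blinded. Much of the eligibility decision is factual or made elsewhere: the clinic makes the diagnosis and prescribes PAP, while AHI, prior programme participation and refusal of PAP leave little room for opinion. At least three people attend the meeting, so one person's guess would have to sway the others.

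A reader might infer that the fidelity rater sits on the eligibility panel, or that a third of allocations were in practice foreseeable there. The documents support neither. The rater is only described as one of the investigators, names are removed so overlap cannot be checked, and neither the extent nor the timing of rating is given. A rating can also only follow allocation and a recorded session, so knowledge arrives late.

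These points reduce the likely size of the problem, and varying the blocks alone does little against guessing. What stands is that several exclusions remain discretionary and no stated safeguard separates knowledge of assignments from the eligibility decision. The claim that envelope storage assures concealment therefore goes further than the safeguards described.

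**Conclusion.** The concern holds as a gap in the stated safeguards, not as evidence that concealment failed. One third certain and 71% guessed right is an upper bound. It needs the block size and full, ordered, timely knowledge of earlier arms within the stratum. With a random 25% to 50% of earlier arms known, the certain share is about 2% to 8% and the best guess is right 55% to 60% of the time.

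That the block size is fixed is inferred from the single size stated. No bias in the adherence comparison can be estimated from the documents. It would also require that a deduced arm changed an eligibility decision, and nothing shows that this happened. The change is worth making because it is cheap and removes most of the exposure.

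**What to change.** 1. State in the protocol that anyone who rates recordings, or otherwise knows assignments, takes no part in deciding eligibility. This is the more important change because it cuts off the information itself. It costs a sentence and, if roles now overlap, a reassignment.
2. For allocations not yet used, have the statistician generate randomly varying block sizes within each AHI stratum (for example 4, 6 and 8), known only to the statistician and left out of the protocol. This needs a new list and new envelopes, and accepts a possible end-of-stratum difference of up to 4 instead of 2.

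The documents do not say how many allocations remain. If none do, the second change no longer applies, and the report should say who knew assignments and who decided eligibility.
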